### BBI608 + Capecitabine

End of Study Visit			≤30 days from last BBI608 dose			X		X	×	X	X	X	X	X	X	X	X		$\mathbf{X}^7$	X	X		
	pı	4	21																				
	z Beyor	3	15	± 1 day																			
1S1	Cycle 2 & Beyond	2	80	± 1																			
ıluatior	Ċ	1	1			×		×	×	X	X	X	X	X		X				X	X	X	×
Study Evaluations		4	21					×	×	X	X	X	X	X				X		X	X	X	
Stı	le 1	3	15	day				×	×	X	X	X	X	X						X	X	X	
	Cycle 1	2	∞	± 1 day				×	×	X	X	X	X	X			X	X		X	X	X	X
		1	1												X							X	
Pre-Study	Evaluation	0	0	-7 ± 3 days	X	X	X	X	×	X	X	X	X	X	X	X	X		$X^6$	X			
Tests & Procedures		Week	Day	Window	Medical history	Physical examination	Serum pregnancy test 	Karnofsky performance status	Vital signs, Weight	Hematology 	Blood chemistry 	Liver function tests 	Electrolytes 	Urinalysis 	12-Lead electrocardiogram	Tumor markers 	Tumor biopsy 	Pharmacokinetics (first six patients only)	Tumor measurement & staging 4,5	Concomitant medications	Adverse events 	Dispense BBI608	Dispense Capecitabine

Confidential

Calculated from the date of first BBI608 dose. Refer to Section 6.3 for description of laboratory assessments.

Ifapplicable

Including tumor measurements, following RECIST 1.1.

Prior to cycle 3 and every other cycle thereafter, assessments must be made utilizing the same imaging method as baseline Unless CT/MRI has been performed within last three weeks.

.1. .2. .3. .2. .7. .8. .9. .7. .8. 

Unless CT/MRI has been performed within last four weeks.

Patients will be followed until resolution of any drug-related AE or SAE occurring during the study or within 30 days of last BBI608 administration.

### 15 APPENDIX C: PERFORMANCE STATUS

ECOG Per	formance status Scale	Karnofsk	xy Performance Scale
Grade	Descriptions	Percent	Description
	Normal activity. Fully active, able to	100	Normal, no complaints, no evidence of disease.
0	carry on all pre-disease performance without restriction.	90	Able to carry on normal activity; minor signs or symptoms of disease.
1	Symptoms, but ambulatory. Restricted in physically strenuous activity, but	80	Normal activity with effort; some signs or symptoms of disease.
1	ambulatory and able to carry out work of a light or sedentary nature (e.g., light housework, office work).	70	Cares for self, unable to carry on normal activity or to do active work.
2	In bed <50% of the time. Ambulatory and capable of all self-care, but unable to	60	Requires occasional assistance, but is able to care for most of his/her needs.
	carry out any work activities. Up and about more than 50% of waking hours.	50	Requires considerable assistance and frequent medical care.
	In bed >50% of the time. Capable of only	40	Disabled, requires special care and assistance.
3	limited self-care, confined to bed or chair more than 50% of waking hours.	30	Severely disabled, hospitalization indicated. Death not imminent.
4	100% bedridden. Completely disabled. Cannot carry on any self-care. Totally	20	Very sick, hospitalization indicated. Death not imminent.
	confined to bed or chair.	10	Moribund, fatal processes progressing rapidly.
5	Dead.	0	Dead.

### 16 APPENDIX D: PHARMACOKINETIC STUDIES

Instructions for Collecting and Processing Samples

Sampling to define the plasma pharmacokinetics of BBI608 and Cetuximab, or Panitumumab or Capecitabine will be performed in the first 6 patients enrolled in each combination arm of the study. For the Cetuximab arm, samples are taken on Day 5-12 and Day 26-33 of cycle 1. For the Panitumumab arm, samples are taken on Day 8-15 and Day 22-29 of cycle 1. For the Capecitabine arm, samples are taken on Day 8-9 and Day 21-22 of cycle 1. The sampling schedule and summary of procedures that are to be used to establish times, collect samples, and process specimens for storage prior to analysis, to insure the acquisition of accurate pharmacokinetic data, are described below. The sampling schedule has been devised to accommodate treatment on an outpatient basis. Dosing of the first dose of drug must be started before 10 a.m. on a Tuesday, Wednesday, or Thursday to facilitate the collection of the pharmacokinetic samples at the scheduled times during the regular operating hours of the outpatient clinics.

Before starting the BBI608 administration, place a large gauge peripheral catheter (e.g., 19 or 20 gauge angiocath straight set with T-connector, or similar IV access device) within a vein in the arm of the subject for the collection of pharmacokinetic blood samples. Patency of the sampling catheter should be maintained between blood draws using either a heparin lock (e.g., 10 U/mL in normal saline) or a slow drip of Normal Saline for Injection, USP (e.g., 10 mL/hr). Extraordinary caution should be taken to prevent hemolysis in the blood sample. Blood may be obtained directly by venipuncture on days when only a single pharmacokinetic blood specimen is scheduled for collection. When sampling through the peripheral catheter, begin to clear the catheter approximately 1 min before the specified sample time by withdrawing the lock solution and approximately 0.5 mL of blood into a syringe. Remove and properly dispose the syringe used to clear the catheter.

A battery-powered digital timer/stopwatch programmed to operate continuously as a 24-hr clock will be used to accurately monitor drug administration and sample collection times. The same timer must be allowed to run without interruption until the last blood specimen has been obtained from the subject during the first cycle of therapy. Timer readings will be noted at the precise time that the administration is started as well as at the beginning and ending times of the blood sample collection intervals. Readings of the digital timer must be directly recorded on a copy of the appropriate Pharmacokinetic Dosing and Blood Collection Time Form.

Please note that blood and plasma must be protected from direct exposure to light and all sample processing procedures are to be performed in a room with indirect lighting. The volume of blood collected for each pharmacokinetic sample will be 3 mL. This volume has shown to be adequate for the pharmacokinetic assay. Samples are to be collected in plastic Vacutainer plasma collection tubes. Immediately wrap the tube with aluminum foil to protect it from exposure to light. Promptly mix the plasma collection tube by gently inverting 6-times, then place it on wet ice, and centrifuge (1,100-1,300 x g, 10 min, 4°C)

within 5-10 min after collection. Separate the plasma from the blood cells using a pipette and transfer approximately equal volumes into three 2 mL self-standing opaque amber polypropylene microcentrifuge cryogenic tubes with external threads. Affix a pre-printed label (protocol number, subject initials, subject number, sample collection date and time) to the cryotube, oriented lengthwise toward the upper part of the tube. Hand-written information on sample tube labels is absolutely prohibited. Completely cover the label with protective cryogenic freezer tape. Place the tube on crushed dry-ice until stored in a freezer maintained at  $\leq$  -70°C. Any deviation from the sample collection time needs to be documented in the study subjects' case report forms and in their study binder.

The total volume of blood collected for pharmacokinetic studies, 100-120 mL, represents < 5% of the total blood volume for a 60 kg subject, during a 28-day treatment cycle. As pharmacokinetic data becomes available during the course of the trial, it may be necessary to modify the number of samples or the times at which they are collected to more accurately define the plasma concentration-time profile of the drug. However, the cumulative volume of blood collected for pharmacokinetic sampling will not exceed 240 mL, or approximately 5% of the total volume of a 60 kg subject during the first 4 weeks of study treatment.

Computer files for dose administration and sample collection time forms and specimen tube labels will be placed in a subdirectory located on a secure network server. All members of the clinical, laboratory, and administrative staff involved with phase II studies will be given read-only access to this subdirectory. The files are placed under the following subdirectories: PK\_Time\_Forms; PK\_Tube\_Labels. Files for the PK time forms are printed directly from the file stored on the network server for each subject study. Since changes may be periodically made to these forms, they cannot be copied onto user personal computers and staff members are instructed not to make photocopies of blank forms. The PK\_Tube\_Label files are templates, and the files are copied to user computers and the limited information pertaining to each subject studied, typically the subject entry no., is added by editing the computer file, then printed onto adhesive-backed labels. Hand-written information on sample tube labels is absolutely prohibited. There are separate sets of labels for blood collection vials and sample storage tubes. Blood collection vials are prelabeled.

Time points will be determined as the difference between the midpoint of the blood collection interval and starting time of dose administration. Concentration-time profiles of BBI608 and Cetuximab, or Panitumumab or Capecitabine will be analyzed by noncompartmental methods and/or nonlinear least squares regression using WinNonlin (Scientific Consulting, Inc.). Pharmacokinetic parameters and variables will be calculated according to standard equations.

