## 5.3.1.2 Week 1 (Cycle 1, Day 5)

- Karnofsky performance status
- Vital signs (weight, pulse)
- Hematology (see Section 6.3)
- Blood chemistry (see Section 6.3)
- Liver function tests (see Section 6.3)
- Electrolytes (see Section 6.3)
- Urinalysis (see Section 6.3)
- Assess AEs
- Record concomitant medication
- Cetuximab, IV infusion starting about 3 hours after morning dose of BBI608
- The second dose of BBI608 will be given approximately 12 hours after the first dose.
- Blood samples for pharmacokinetics, (for only the first 6 patients enrolled in this arm).
- Dispense BBI608 (one week supply)

Blood samples for pharmacokinetics will be collected immediately prior to the first dose of BBI608 and will continue through 171 hours after administration of the first dose of BBI608. Specific details for the collection of blood samples for pharmacokinetics can be located in Sections 6.4 and Section 16.

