8.2.3.1.2. Pharmacokinetic parameters

PK parameters for napabucasin, including maximum concentration at steady state (Cmax,ss), the timepoint when Cmax was observed (Tmax), area under the plasma concentration time curve during a dosing interval at steady state (AUCtau), minimum concentration at steady state (Cmin,ss), total body clearance at steady state (CLss/F), volume of distribution during terminal elimination phase at steady state (Vz/F), and terminal elimination half-life (t1/2) will be listed and summarized using descriptive statistics, including N, mean, standard deviation, CV, geometric mean, geometric CV, minimum, maximum, and median. For Tmax, N, minimum, maximum, and median will be reported. Parameters will be summarized by day, napabucasin dose, concomitant therapy and cohort.

PK parameters for capecitabine and metabolite 5-FU, including maximum concentration after a single dose (Cmax), the timepoint when Cmax was observed (Tmax), area under the plasma concentration time curve from zero to the last quantifiable concentration (AUClast), area under the plasma concentration time curve from zero extrapolated to infinity (AUCinf), total body clearance (CL/F) volume of distribution during the terminal elimination phase (Vz/F), and t½, will be listed and summarized using descriptive statistics, including N, mean, standard deviation, CV, geometric mean, geometric CV, minimum, maximum, and median. For Tmax, N, minimum, maximum, and median will be reported. Parameters will be summarized by day and napabucasin dose.

Napabucasin PK parameters will be estimated using actual elapsed time from napabucasin dosing. PK parameters of capecitabine and metabolite 5-FU will be estimated using actual elapsed time from capecitabine dosing. Imputation of concentration data for BLQ is described in Section 7.5.

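### On two of its three permitted weekdays, the PK start-day rule puts cetuximab- and panitumumab-arm draws on a weekend, so the lone 99 h sample may be missed or mistimed

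*Protocol*

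**What the plan says.** Protocol Appendix D states that dosing "must be started before 10 a.m. on a Tuesday, Wednesday, or Thursday to facilitate the collection of the pharmacokinetic samples at the scheduled times". The purpose is given in the same sentence: draws are to be made "at the scheduled times during the regular operating hours of the outpatient clinics".

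The Appendix D sampling tables for the cetuximab arm (Arm A) and the panitumumab arm (Arm B) list draws up to 540 min, then at 24 h, 27 h, 99 h and 171 h. The capecitabine arm (Arm C) has no draw after 24 h. Each patient has two profiles: "For the Cetuximab arm, samples are taken on Day 5-12 and Day 26-33 of cycle 1" and "For the Panitumumab arm, samples are taken on Day 8-15 and Day 22-29 of cycle 1". Sampling "will be performed in the first 6 patients enrolled in each combination arm of the study".

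Appendix D does not say which first dose the weekday rule governs. The Day 5 visit in protocol 5.3.1.2 says that sampling "will continue through 171 hours after administration of the first dose of BBI608". BBI608 has by then been taken since Day 1, so the phrase there must mean that day's morning dose. Protocol 10.6, by contrast, counts its sampling days from the first dose of Cycle 1.

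**The concern.** The weekday restriction exists to keep draws inside clinic hours. In Arms A and B it appears to work against that aim, because a draw four days after a Tuesday or Wednesday cannot fall on a weekday. The draw affected, PK-14 at 99 h, is the only one between 27 h and 171 h. It serves the antibody PK profile that protocol 2.2 lists as a secondary objective, and protocol 10.6 plans terminal half-life and AUC from these profiles. If PK-14 is missing, the late part of the antibody curve rests on the 24 h and 27 h samples and the 171 h sample, with 171 − 27 = 144 h between them. Only six patients per arm are sampled.

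**Working it through.** The plan gives no figure to reproduce. The check is calendar arithmetic on its own schedule.

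**Inputs.** Permitted starts: Tuesday, Wednesday or Thursday before 10 a.m. (Appendix D). Late draws in Arms A and B: 24, 27, 99 and 171 h after the BBI608 dose (Appendix D tables). PK days: Day 5 and Day 26 (A), Day 8 and Day 22 (B), Day 8 and Day 21 (C).

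**1. Day of each draw.** Day offset = floor((clock time of dose + sample hour) / 24). The sample hours are 24 = 1 × 24, 27 = 1 × 24 + 3, 99 = 4 × 24 + 3 and 171 = 7 × 24 + 3. A dose before 10 a.m. plus 3 h ends before 1 p.m., so no draw crosses midnight. The offsets are +1, +1, +4 and +7 days.

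**2. If the rule governs the PK-day morning dose (Arms A and B).**

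| PK day | 24 h and 27 h | 99 h | 171 h |
|---|---|---|---|
| Mon (not permitted) | Tue | Fri | Mon |
| Tue | Wed | **Sat** | Tue |
| Wed | Thu | **Sun** | Wed |
| Thu | Fri | Mon | Thu |
| Fri (not permitted) | **Sat** | Tue | Fri |

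Only Monday and Thursday keep all draws on weekdays, and only Thursday is permitted.

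**3. Second profile.** Arm A: 26 − 5 = 21 days = 3 weeks. Arm B: 22 − 8 = 14 days = 2 weeks. The second profile has the same weekday and the same difficulty.

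**4. If the rule governs Cycle 1 Day 1.** In Arm B, Day 8 has the weekday of Day 1, so step 2 is unchanged. In Arm A, Day 5 is Day 1 + 4:

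| Day 1 | Day 5 and Day 26 | 24 h and 27 h | 99 h | 171 h |
|---|---|---|---|---|
| Tue | **Sat** | **Sun** | Wed | **Sat** |
| Wed | **Sun** | Mon | Thu | **Sun** |
| Thu | Mon | Tue | Fri | Mon |

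Two of the three permitted days again put draws on a weekend, this time including the intensive sampling day.

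**5. Other fixed days in Arm A.** Day 1 (dispensing and an ECG 2 h after the first dose, protocol 5.3.1.1) and Day 8 (optional biopsy, 5.3.1.3) are seven days apart, so they share a weekday. With Day 5 on Tuesday, Wednesday or Thursday they fall on Friday, Saturday or Sunday. At nominal study days, therefore, no permitted PK day keeps Day 1, Day 8 and every draw on weekdays. With Day 5 on Monday, Days 1 and 8 are Thursdays and the draws fall on Mon, Tue, Fri and Mon.

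**6. Arm C.** 21 − 8 = 13 days, so the second profile is one weekday earlier. Day 8 on Tue, Wed or Thu gives Day 21 on Mon, Tue or Wed, and the 24 h draws fall on the next day. None is on a weekend.

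**7. Size.** PK-14 is one of 15 samples per profile, so 2 of 30 per patient. Over both arms there are 6 × 2 × 2 = 24 PK-14 draws.

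**The case against.** Much of the case on the other side stands.

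- **Loss is not established.** A reader might infer that the 99 h sample will be lost. The documents do not say that clinics are closed at weekends or that an off-time sample is discarded. The rule is worded as an aid to collection, not a guarantee. "Any deviation from the sample collection time needs to be documented", and Appendix D derives each time point from the actual collection interval. On the SAP side, "Napabucasin PK parameters will be estimated using actual elapsed time from napabucasin dosing". A draw moved to the same clock time on Friday or Monday would come at 75 h or 147 h after a Tuesday start, and at 51 h or 123 h after a Wednesday start. Each is still a usable point inside the gap. Appendix D also allows sampling times to be revised as PK data accumulate.
- **The visit window helps.** Appendix A gives Cycle 1 visits ±1 day. If the rule governs the PK day, a nominal Wednesday can move to Thursday. If it governs Day 1, Arm B can move Tuesday to Monday or Wednesday to Thursday, and Arm A with a Wednesday start can move Day 5 from Sunday to Monday. Arm A with a Tuesday start stays stuck: Day 5 moves from Saturday only to Friday, which puts 24 h and 27 h on Saturday, or to Sunday. The window is stated for visits, not for individual draws.
- **A number for the harm is tempting but unsupported.** With evenly spread start days, 24 × 2/3 = 16 PK-14 draws would fall on a weekend. Sites may choose Thursday throughout, or never, so the possible range is 0 to 24. Similarly, assume mono-exponential decline at rate k and complete loss of the sample. The linear-trapezoid error over the gap is then [(C24 + C168)/2 × 144] / [(C24 − C168)/k] − 1, with times counted from the start of infusion. It is 15.5%, 5.7% or 2.9% for assumed half-lives of 3, 5 or 7 days, against 4.0%, 1.4% or 0.7% with the sample. The plan does not specify linear trapezoids, and a log-linear rule would give zero error under the same assumption. These figures are illustrations only.
- **The SAP does not use the sample.** SAP 3.2, 6.4 and 8.2.3.1.2 define PK endpoints, sets and parameters for napabucasin, capecitabine and 5-FU only. Napabucasin AUC is taken over one dosing interval.

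**Conclusion.** The rule and the sampling tables are inconsistent, at a minor level. In Arms A and B, two of the three permitted weekdays put scheduled draws on a weekend under either meaning of first dose. On the meaning supported by protocol 5.3.1.2, the draw affected is PK-14 in both profiles. It may be missed or mistimed, which weakens the antibody half-life and AUC that the protocol names (2.2, 10.6 and Appendix D). No SAP-defined PK parameter and no efficacy result is affected.

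The conclusion assumes nominal study days and draw times, and that regular clinic hours exclude weekends, which the documents imply but do not state. It does not extend to certain loss of the sample or to any particular bias in AUC.

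**What to change.** Amend the sentence in Appendix D so that the weekday rule refers to the first PK day (Day 5 in Arm A, Day 8 in Arms B and C) and is set by arm:

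- **Arm A:** Monday. Days 1 and 8 are then Thursdays and all draws fall on weekdays. A Thursday PK day would need the visit window to keep Day 1 off a Sunday.
- **Arm B:** Monday or Thursday.
- **Arm C:** keep the present weekdays.

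Also state whether the ±1 day window applies to individual draws. Study days, sampling times and doses are unchanged. The cost is a short edit and fewer start weekdays for the six PK patients in each antibody arm.

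If PK sampling is already complete, report how many 99 h samples were missed or taken off-time, with the actual times, alongside any antibody PK that is presented.

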### Pharmacokinetic Sample Collection (Cetuximab Arm)

### Day 5-12 in CYCLE 1 ONLY

Cycle No.	Procedure	Sample No.	Desired Time
1	Draw blood sample	PK-01	-5 min
	Start BBI608 administration		0 min
	Draw blood sample	PK-02	30 min
	Draw blood sample	PK-03	60 min
	Draw blood sample	PK-04	120 min
	Draw blood sample	PK-05	175 min
	Start Cetuximab infusion		180 min
	Draw blood sample	PK-06	240 min
	Draw blood sample	PK-07	300 min
	Draw blood sample	PK-08	360 min
	Draw blood sample	PK-09	420 min
	Draw blood sample	PK-10	480 min
	Draw blood sample	PK-11	540 min
	Draw blood sample	PK-12	24 hour
	Draw blood sample	PK-13	27 hour
	Draw blood sample	PK-14	99 hour
	Draw blood sample	PK-15	171 hour

Day 26-33 in CYCLE 1 ONLY

Cycle No.	Procedure	Sample No.	Desired Time
1	Draw blood sample	PK-01	-5 min
	Start BBI608 administration		0 min
	Draw blood sample	PK-02	30 min
	Draw blood sample	PK-03	60 min
	Draw blood sample	PK-04	120 min
	Draw blood sample	PK-05	175 min
	Start Cetuximab infusion		180 min
	Draw blood sample	PK-06	240 min
	Draw blood sample	PK-07	300 min
	Draw blood sample	PK-08	360 min
	Draw blood sample	PK-09	420 min
	Draw blood sample	PK-10	480 min
	Draw blood sample	PK-11	540 min
	Draw blood sample	PK-12	24 hour

Draw blood sample	PK-13	27 hour
Draw blood sample	PK-14	99 hour
Draw blood sample	PK-15	171 hour

### Pharmacokinetic Sample Collection (Panitumumab Arm)

### Day 8-15 in CYCLE 1 ONLY

Cycle No.	Procedure	Sample No.	Desired Time
1	Draw blood sample	PK-01	-5 min
	Start BBI608 administration		0 min
	Draw blood sample	PK-02	30 min
	Draw blood sample	PK-03	60 min
	Draw blood sample	PK-04	120 min
	Draw blood sample	PK-05	175 min
	Start Panitumumab infusion		180 min
	Draw blood sample	PK-06	240 min
	Draw blood sample	PK-07	300 min
	Draw blood sample	PK-08	360 min
	Draw blood sample	PK-09	420 min
	Draw blood sample	PK-10	480 min
	Draw blood sample	PK-11	540 min
	Draw blood sample	PK-12	24 hour
	Draw blood sample	PK-13	27 hour
	Draw blood sample	PK-14	99 hour
	Draw blood sample	PK-15	171 hour

### Day 22-29 in CYCLE 1 ONLY

Cycle No.	Procedure	Sample No.	Desired Time
1	Draw blood sample	PK-01	-5 min
	Start BBI608 administration		0 min
	Draw blood sample	PK-02	30 min
	Draw blood sample	PK-03	60 min
	Draw blood sample	PK-04	120 min
	Draw blood sample	PK-05	175 min
	Start Panitumumab infusion		180 min
	Draw blood sample	PK-06	240 min

Draw blood sample	PK-07	300 min
Draw blood sample	PK-08	360 min
Draw blood sample	PK-09	420 min
Draw blood sample	PK-10	480 min
Draw blood sample	PK-11	540 min
Draw blood sample	PK-12	24 hour
Draw blood sample	PK-13	27 hour
Draw blood sample	PK-14	99 hour
Draw blood sample	PK-15	171 hour

### Pharmacokinetic Sample Collection (Capecitabine Arm)

### Day 8-9 in CYCLE 1 ONLY

Cycle No.	Procedure	Sample No.	Desired Time
1	Draw blood sample	PK-01	-5 min
	Start BBI608 administration		0 min
	Draw blood sample	PK-02	30 min
	Draw blood sample	PK-03	60 min
	Draw blood sample	PK-04	120 min
	Start Capecitabine administration		175 min
	Draw blood sample	PK-05	180 min
	Draw blood sample	PK-06	240 min
	Draw blood sample	PK-07	300 min
	Draw blood sample	PK-08	360 min
	Draw blood sample	PK-09	420 min
	Draw blood sample	PK-10	480 min
	Draw blood sample	PK-11	540 min
	Draw blood sample	PK-12	600 min
	Draw blood sample	PK-13	660 min
	Draw blood sample	PK-14	24 hour

### Pharmacokinetic Sample Collection (Capecitabine)

Day 21-22 in CYCLE 1 ONLY

Cycle No.	Procedure	Sample No.	Desired Time
1	Draw blood sample	PK-01	-5 min

Start BBI608 administration		0 min
Draw blood sample	PK-02	30 min
Draw blood sample	PK-03	60 min
Draw blood sample	PK-04	120 min
Start Capecitabine administration		175 min
Draw blood sample	PK-05	180 min
Draw blood sample	PK-06	240 min
Draw blood sample	PK-07	300 min
Draw blood sample	PK-08	360 min
Draw blood sample	PK-09	420 min
Draw blood sample	PK-10	480 min
Draw blood sample	PK-11	540 min
Draw blood sample	PK-12	600 min
Draw blood sample	PK-13	660 min
Draw blood sample	PK-14	24 hour

